# 2.3 HIFU: International Experience with Prostate Cancer Treatment

HIFU therapy has been a mainstay of prostate cancer care in Europe, Canada, and Mexico for the last fifteen years, and cancer control and side effect outcomes have been very

promising. A review of the randomized clinical trials, meta-analyses, and systematic reviews reporting on efficacy and safety of HIFU as primary treatment was recently reported, though this review included a mixed population with regard to tumor mix and ablation zone (whole-gland and hemigland). 5-year disease free survival rates were 61-95%. Common complications associated with HIFU were urinary retention (<1-20%), UTI (2-48%), stress urinary incontinence of any degree (<1-34%), and erectile dysfunction (20-86%). Rare complications included recto-urethral fistula (<2%), bladder neck stenosis, urethral stricture, perineal pain, urinary obstruction, epididymitis, and prostatitis. The largest institutional series of hemigland HIFU for low- (25%) and intermediate-risk (75%) prostate cancers suggested even better results, with return of erectile function for penetrative sex in 95% of men, 90% pad-free and leak-free continent, and 89% had no histological evidence of cancer at 6 months. 89% of men reached the trifecta status of pad-free, leak-free continence, erections sufficient for intercourse, and cancer control at 12 months.(8) True focal therapy is in a nascent stage of development, but early results are similar to hemigland treatment. In a prospective study of 42 men with low- and intermediate-risk cancer at University College London, 95% (95% CI 83-99%) were cancer free on biopsy at 12 months and 84% (95% CI 66–95%) reached trifecta status.(9) These results, though admittedly in highly selected populations, are clear improvements on cancer control and quality of life outcomes in modern surgical and radiation cohorts.

# 2.4 MRI for Prostate Cancer Imaging

Multiparametric MRI (mpMRI) combining T2-weighted, diffusion-weighted, and dynamic contrast enhanced (DCE) images is quickly becoming part of the standard of care for detection and localization of prostate cancer.(10, 11) Prostate MRI has been shown to have high sensitivity and specificity for high-grade prostate cancers, with approximately 80% false negative rate for detection of Gleason 7 or higher tumors. The Prostate Imaging-Reporting and Data System (PI-RADS) scoring system is a widely accepted rating system for estimating risk of cancer, using a 1–5 scale to provide clinicians with an estimate for likelihood of cancer; this scale uses T2-weighted imaging, diffusion weighted imaging, dynamic contrast-enhancement, and MRI spectroscopy to inform this assessment. Some variations on this scale, such as the UCLA prostate MRI scoring system, give more weight to the diffusion-weighted imaging component, since it is the component providing the most predictive utility.

Diffusion-weighted imaging (DWI) is sensitive to the diffusion of water molecules interacting with surrounding macromolecules. DWI, which provides a quantitative biological parameter called apparent diffusion coefficient (ADC) value, is a robust MRI parameter for differentiating benign and malignant prostate tissue.(12, 13) In fact, the latest version of the Prostate Imaging-Reporting and Data System (PI-RADS) scoring system relies almost exclusively on DWI to identify tumors in the peripheral zone, which is where the vast majority of prostate cancers form. Findings on T2 images are not used to identify cancer, and DCE images are only used to differentiate between some PI-RADS 3 and 4 lesions. In a pilot study of prostate cancer AS, DW-MRI was useful for detecting progression of Gleason score based on changes in ADC value.(14) Tumor size is an important clinical criterion for defining low risk prostate cancer, and tumor size based on DWI has been shown to crudely predict low risk prostate cancer.(15) However, conventional DWI using single-shot echo-planar imaging is unable to detect small tumors(16) or detect small changes in tumor size on serial imaging.

# 2.5 High-Resolution Prostate MRI (hrMRI)

Over the last several years, our group at Cedars-Sinai has developed technology to improve resolution of standard mpMRI, allowing for improved detection of smaller tumors. (1, 2) By using a three-dimensional (3D) high-resolution diffusion-weighted imaging sequence (HR-DWI), image quality is improved and confers a 5-fold improvement in resolution when compared to standard two-dimensional (2D) DWI (S-DWI). This novel 3D DWI technique has been developed by our team and can be applied on existing 1.5T or 3T MRI systems. S-DWI suffers from two important limitations. a) It uses single-shot echoplanar imaging (EPI) for data acquisition, which produces magnetic susceptibility induced streaking artifacts and geometric distortions so that round objects may appear oval. b) The relatively low signal-to-noise ratio and 2D image acquisition with S-DWI limit spatial resolution, which is defined by the minimum distance between two objects required to resolve them uniquely. Our hrMRI incorporating HR-DWI overcomes these limitations by using magnetization prepared, multi-shot, turbo-spin-echo acquisition, which improves signal-to-noise ratio (SNR), spatial resolution, and image quality, and eliminates geometric distortions and streaking artifacts associated with EPI.

In a prospective study assessing the performance of hrMRI in 17 prostate cancer patients on active surveillance, the technique was shown to detect tumors not seen on standard mpMRI. Standard mpMRI predicted biopsy results (AUC 0.72, Fisher's exact p<0.001), but high-resolution DWI sequences allowed MP-MRI to be more highly predictive of biopsy results (AUC 0.88, Fisher's exact p<0.001). hrMRI had a sensitivity of 95.7% and identified tumor in 22 of 23 zones proven to have cancer on biopsy. In contrast, standard mpMRI had a sensitivity of 60.9% and only identified 14 of 23 biopsy-positive zones (p=0.004). In all, hrMRI was shown to detect 60% of tumors not seen on standard MRI.

## 2.6 PSMA and PET-MRI in Prostate Cancer

Positron emission tomography (PET) imaging has been increasingly used for detection of occult distant metastases in patients with advanced prostate cancer using prostate-cancer-specific radiotracers (PSMA) or radiotracers that accumulate preferentially within prostate cancer tissue (11C choline, 11C acetate, and 18F fluciclovine). Prostate-specific membrane antigen (PSMA) is a type II membrane protein originally characterized by the murine monoclonal antibody (mAb) 7E11-C5. 3 and is expressed in all forms of prostate tissue, including carcinoma. F18-PSMA is a radiolabeled antibody that binds to PSMA antigen expressed on the surface of the prostatic cancer cells.

While PET technology is usually paired with CT imaging for 3D localization due to wide availability of CT technology, there have been efforts to pair PET technology with MRI to improve identification of lesions both within and outside of the prostate gland, given the advantages in spatial resolution of MRI over CT imaging. While mpMRI is a very sensitive imaging modality for identifying localized prostate cancers, its specificity is limited; colocalization of tumors identified on MRI with PET imaging may be able to improve specificity to account for this limitation.

Early work has suggested that co-localization of this PET radiotracer with 3-D mpMRI imaging may enhance accuracy of localization of intraprostatic cancer lesions compared with mpMRI or PET/CT alone. In a study of 21 patients who underwent 18F-fluciclovine PET/CT and mpMRI prior to radical prostatectomy, combined 18F-fluciclovine PET/CT and mpMRI imaging yielded a positive predictive value of 82% for tumor localization, which

was significantly higher than that with either modality alone.

This would suggest that pairing also F18-PSMA PET imaging with MRI directly may improve localization of cancers within the prostate for HIFU treatment planning. We hypothesize that further leveraging the sensitivity and spatial resolution of hrMRI with the specificity of PET imaging may further enhance performance in accurately identifying cancers within the prostate.

# 2.7 MR/US-Fusion for Targeting of Prostate Cancers

The advent of improved prostate imaging using multiparametric MRI and PET have dovetailed with advances in fusion software platforms that offer the ability to overlay static MRI images with real-time ultrasound images at the time of biopsy. This technology, called MR-US fusion, allows clinicians to target potential regions of interest in the prostate seen on mpMRI during an transrectal ultrasound-guided biopsy. Targeted MR-US fusion biopsies have been shown to significantly improve sensitivity and overall accuracy of biopsy over standard sextant biopsy by 24% and 14%, respectively. Most academic centers now offer MR-US fusion biopsies for patients with persistent rising PSA after negative standard biopsy and for surveillance biopsies while on active surveillance. MR-US fusion techniques are also being applied to focal ablation of prostate cancers with HIFU; both the Sonablate and Ablatheram HIFU platforms have announced partnerships with MR-US fusion companies to provide targeting during tumor ablation with HIFU. However, despite these improvements, the accuracy of targeted biopsy and targeted focal therapy is necessarily limited by accuracy of the MRI imaging for detection and localization of lesions.

# 2.8 Combining MR/US-Fusion, hrMRI, and PET-MRI with HIFU for Focal Treatment of Prostate Cancer

Because the oncological effectiveness of HIFU depends on robust mapping and targeting of lesions within the prostate, improved detection of lesions using hrMRI and/or PET-MRI could provide a significant advantage in HIFU cancer control outcomes. Patients who are eligible for hemigland and focal HIFU absolutely depend on imaging for treatment planning; for example, in a patient with an index lesion of the right side of the prostate only, if imaging fails to detect a small focus of prostate cancer present on the left, hemigland HIFU (only treating the right side of the prostate) will not be effective at eradicating the entire bulk of his disease. It is even more important to accurately identify all prostate cancers when mapping for true focal therapy, since only identified lesions are ablated. We have previously shown that hrMRI detects up to 60% of tumors within the prostate not seen on mpMRI, and PET-MRI techniques may be able to improve the accuracy of this detection. Even if lesions that are ignored by mpMRI but detected on PET-hrMRI are indolent, long-term growth of these lesions may certainly affect cancer control outcomes over time and require costly and morbid retreatment. We believe that improved imaging at the outset of focal therapy would provide more comprehensive eradication of cancer burden from the start, resulting in improved long-term outcomes.

# 2.9 PET-hrMRI prior to prostatectomy

An important limitation of studying a new imaging modality in patients undergoing HIFU is that tumors are identified by biopsy, which is susceptible to sampling error. In other words, tumors invisible on MRI and missed on systematic prostate biopsy are not considered in

defining the limitation of our novel imaging. These tumors are expected to be small, low grade tumors that do not require treatment. However, future research will need to consider appropriate surveillance strategies for these MRI-invisible tumors. To define sensitive of PET-hrMRI, we would need to know where all the tumors are. Therefore, a pilot study is included in which patients scheduled to undergo radical prostatectomy will have a preoperative PET-hrMRI. The prostatectomy pathology will be the reference standard. Since the true location of all tumors will be known, both the sensitivity and specificity of PSMA-PET MRI can be determined.

#### 3.0 STUDY DESIGN:

#### 3.1 Overview

This prospective trial will evaluate the effectiveness of F18-PSMA PET-hrMRI versus standard mpMRI at identifying prostate cancer targets for HIFU therapy. Patients with clinically localized, Gleason score 7-10 prostate cancer localized to one lobe on prior biopsies or overall Gleason score 6 with ≥ half of systematic biopsy cores positive and ≥ 50% of core involvement in at least one core, interested in HIFU would receive both a standard mpMRI and F18-PSMA PET-hrMRI. They would then undergo a mapping biopsy using a standard sextant template plus MR/US-fusion targeted biopsy of any lesions with PI-RADS scores ≥3 on hrMRI or 18F-PSMA PET positivity. The primary endpoint of the Phase II study would assess the number of biopsy-proven cancers that mpMRI would have missed compared with hrMRI and/or F18-PSMA PET. Following our tumor mapping study, patients with high grade disease (i.e. Gleason grade 4 or 5) in one lobe undergo hemigland or focal HIFU of that lobe. At 6 months, patients would undergo repeat mpMRI and prostate biopsy (MR/US-fusion biopsy plus standard sextant biopsy) to assess the negative biopsy rate in the treated region and absence of Gleason grade 4 or 5 in the untreated region which will be the secondary endpoint of the Phase II study.

As the gold standard for evaluation of sensitivity and specificity of any imaging test is the pathologic analysis of the whole prostatic gland obtained at prostatectomy (as the biopsy is subject to error sampling), a concurrent pilot study will enroll patients scheduled to undergo prostatectomy with the primary endpoint to define sensitivity of PET-hrMRI versus mpMRI compared against the prostatectomy pathology and with the secondary endpoint define specificity of hrMRI, F18-PSMA PET and mpMRI for detecting all tumors and metastasis at 6 months follow up.

## 3.2 Study Population

The study population for recruitment will be patients within the academic urology practice at Cedars-Sinai Medical Center. After initial visit, any patient with clinically localized prostate adenocarcinoma with Gleason score 7-10 prostate cancer localized to one lobe on prior biopsy desiring therapy with HIFU may be considered a potential study participant. Subjects with newly diagnosed disease or on active surveillance may be considered.

#### 3.2.1 Inclusion Criteria

- 1. Biopsy consisting of ≥ 10 tissue cores sampled
- 2. PSA <20 ng/mL (for HIFU arm only)
- 3. cT1-cT2c

- 4. Either overall Gleason score ≥ 7 with Gleason grade 4 or 5 component localized to one lobe (i.e. right or left) OR overall Gleason score 6 with ≥ half of systematic biopsy cores positive and ≥ 50% of core involvement in at least one core (for HIFU arm only)
- 5. Patient considering focal HIFU therapy or robotic radical prostatectomy

#### **3.2.2** Exclusion criteria:

- 1. Previous local therapy for prostate cancer
- 2. Inability to receive PET tracer
- 3. Inability to receive MRI
- 4. Estimated glomerular filtration rate (GFR) <15 mL/min/1.73 m^2
- 5. Any other condition which, in the investigator's option, may make the patient a poor candidate for participation in a clinical trial.

## 3.3 Study endpoints

Primary Endpoint (HIFU): Number of additional biopsy-proven cancers that novel imaging modalities of hrMRI and/or F18-PSMA PET would detect when compared to reference standard imaging of mpMRI in patients undergoing HIFU procedure.

Secondary Endpoint (HIFU): Negative biopsy rate on standard 12-core biopsy 6 months following HIFU therapy.

**Primary Endpoint (Prostatectomy):** To determine the sensitivity in detection of prostatic carcinoma of novel imaging modalities of hrMRI and/or F18-PSMA PET compared to reference standard mpMRI in patients scheduled to undergo radical prostatectomy.

Secondary Endpoint (Prostatectomy): Specificity of hrMRI, F18-PSMA PET and mpMRI for detecting all tumors and metastasis at 6 months follow up.

**Exploratory Endpoint:** RNAseq transcriptome analysis of lesions that are positive on mapping biopsy. Sensitivity and specificity of PET-hrMRI for detecting all tumors detected on prostatectomy pathology.

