# **STUDY SUMMARY**

Title	High-Resolution, 18F-PSMA PET-MRI for Mapping Prostate Cancer in Patients Considering Focal High-Intensity Focused Ultrasound (HIFU) Therapy or Radical Prostatectomy
Short Title	High resolution PET-MRI before prostate cancer HIFU or radical prostatectomy
Protocol Number	Pro00000832
Phase	Two parts: Phase II and Pilot
Methodology	Single arm, paired imaging (Phase II)
Study Duration	3 years
Study Center(s)	Cedars Sinai Medical Center
Objectives	Phase II Study (HIFU): Primary Endpoint: Number of additional biopsy-proven cancers that novel imaging modalities of hrMRI and/or F18-PSMA PET would detect when compared to reference standard imaging of mpMRI in patients undergoing HIFU procedure. Secondary Endpoint: Negative biopsy rate of standard 12-core biopsy 6 months following HIFU therapy.  Phase II Study (Radical Prostatectomy(RP)): Primary Endpoint: To determine the sensitivity in detection of prostatic carcinoma of novel imaging modalities of hrMRI and /or F18-PSMA PET compared to reference standard mpMRI in patients scheduled to undergo radical prostatectomy. Secondary Endpoint: Specificity of hrMRI, F18PSMA PET and mpMRI for detecting all tumors and metastasis at 6 months follow up.
Number of Subjects	30 Study Subjects (Phase II HIFU), 31 Study Subjects (Phase II RP)

Diagnosis and Main Inclusion Criteria	
 
Diagnosis for Pilot trial: Any patient scheduled to undergo radical prostatectomy Diagnosis: Clinically localized, unilateral, high-grade prostate cancer OR at high risk for having unrecognized high grade Prostate Cancer Inclusion Criteria:         
 
Biopsy consisting of ≥ 10 tissue cores sampled
 
PSA ≤20 ng/mL
 
cT1-cT2c
 
Either overall Gleason score ≥ 7 with Gleason grade 4 or 5 component localized to one lobe (i.e. right or left) OR overall Gleason score 6 with ≥ half of systematic biopsy cores positive and ≥ 50% of core involvement in at least one core
 
Patients considering focal HIFU therapy
 
Patients considering radical prostatectomy
 
 
 
		
Study Imaging	F18-PSMA PET-MRI in combination with multiparametric prostate MRI using high resolution DWI		
Control Imaging	Standard multiparametric prostate MRI		
Reference standard	MRI-targeted prostate biopsies will serve as the reference standard and all lesions seen on any MRI protocol will be biopsied. In the pilot trial, the prostatectomy pathology will serve as the reference standard.		

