# **3.4.2** Study Calendar for Focal High-Intensity Focused Ultrasound (HIFU) Therapy

Procedure	Screening	lmaging	Post- imaging²	Standard of Care (SOC) Treatment	Post SOC Treatment 6 months (+/- 1.5 months) following HIFU
Informed Consent/Registration	X				
Review Eligibility	X				
Demographics	X				
Medical History	X				
Prior and Current Medication Review	Х				
Vital Signs 		X	X		
Physical Exam (including symptoms assessment, height, weight) 	Х				
Standard MRI with Gadolinium		X (at least one day prior to targeted prostate biopsy)			X (at least one day prior to targeted prostate biopsy)
Optional: Tissue collection 			Х		Х
Optional: Blood collection 	X 	X 7	X 	X 	X8

18-PSMA PET-hrMRI	X (at least one day prior to targeted prostate biopsy)			
Adverse Event Review	X	X	X	X
Hemigland or Focal High Intensity Focused Ultrasound (HIFU) 			X (performed within 4 months after mapping and/or targeted prostate biopsy)	
Standard Sextant Mapping Biopsy		X		Х
MR/US-fusion targeted biopsy		X 3		Х

- 1. Focal HIFU performed on study for patients with confirmed unilateral high grade prostate cancer.
- 2. End of study for bilateral Gleason ≥7 disease
- 3. Of any lesions with PI-RADS scores >3 on hr MRI or 18F-PSMA PET positivity
- 4. Tissue collection includes left over tissue from standard of care collection only.
- 5. Need to be obtained within 180 days of screening. Vital signs will be assessed before and after administration of 18F-DCFPyL.
- 6. Blood collection will be approximately 17 mL (approximately 1 tablespoon) of whole blood. As of August 2023, optional blood draw has been removed from ICF (MODCR00000250).
- 7. Pre-treatment blood will be drawn once before HIFU or on the day of surgery with standard of care blood draw.
- 8. Post-treatment blood will be drawn once after HIFU with standard of care blood draw.

Study Calendar for Radical Prostatectomy

Procedure	Screening	lmaging	Standard of Care (SOC) Treatment	Post SOC Treatment 6 months (+/- 1.5 months) following Prostatectomy
Informed Consent/Registration	Х			
Review Eligibility	X			
Demographics	X			
Medical History	X			
Prior and Current Medication Review	Х			
Vital Signs 		X		
Physical Exam (including symptoms assessment, height, weight) 	Х			

Standard MRI with Gadolinium		X (preoperative PET-hrMRI prior to prostatectomy)		
Optional: Tissue collection 			Χ	

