Optional: Blood collection 	X 	X 4	X 	
18-PSMA PET- hrMRI		X (at least one day prior to prostatectomy)		
PSA Lab Result				X
Adverse Event Review		X	Х	Х
Prostatectomy			Х	

- 1. Tissue collection includes left over tissue from standard of care collection only.
- 2. Need to be obtained within 180 days of screening. Vital signs will be assessed before and after administration of 18F-DCFPyL.
- 3. Blood collection will be approximately 17 mL (approximately 1 tablespoon) of whole blood. As of August 2023, optional blood draw has been removed from ICF (MODCR00000250).
- 4. Pre-treatment blood will be drawn once before prostatectomy or on the day of surgery with standard of care blood draw.
- 5. Post-treatment blood will be drawn once after prostatectomy with standard of care blood draw.

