## Pre-HIFU Imaging Protocol for Tumor Mapping

Eligible participants will then undergo mapping MRI in advance of HIFU therapy using both standard mpMRI and PET-hrMRI. All imaging will be completed in one sitting. hrMRI increases the length of the MRI by approximately 5 minutes. PET-MRI sequences increased the length of mpMRI by 30 minutes. Scanning will be done on the Siemens Biograph mMR scanner at the Research Imaging Core facility in the Davis Building.

Subjects undergoing a PET-hrMRI will be screened using the standard clinical protocol to determine whether it is safe to administer contrast to the subject.

PET scans involve injection of a radioisotope. Subjects undergoing a contrast-enhanced MR-PET will be screened using the standard clinical protocol to determine whether it is safe to administer contrast to the subject. An IV line will be inserted, and the participant will receive 9 mCi ±20% F18-PSMA injection diluted up to 10mL injected via the IV, as an IV bolus injection followed by 10mL flush with normal saline solution. The participant will then be positioned supine in the scanner and will be scanned in the area of the prostate. The time from end of injection of F18-PSMA injection to the start of imaging should be 60 minutes. For the PET acquisition, participants will be imaged for approximately 30 minutes.

All MRI images will be read according to PI-RADS (version 2) by a dedicated GU radiologist who has experience reading over 500 prostate MRIs. All PET scans will be read by nuclear medicine investigators on the study ([name]). All lesions with PI-RADS greater than or equal to 3 and all PET positive areas will be considered suspicious for cancer. A region of interest (ROI) application will be used. The circumference of a

suspicious lesion will be drawn on each individual MRI slice. The lesion volume and average ADC will be calculated from the ROI's. The tumor volumes and ADCs will be provided by the radiologist. To prevent the hrMRI from influencing the review of the mpMRI, all mpMRI's will be reviewed first. The radiologist will always be blinded to previous pathology.

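### The prostatectomy secondary endpoint promises specificity for metastasis at 6 months without a test to verify it, and Section 6.2 does not state the unit for tumor specificity

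*Combined protocol and SAP*

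**What the plan says.** - **Endpoint.** Section 3.3 gives the RP secondary endpoint as "Specificity of hrMRI, F18-PSMA PET and mpMRI for detecting all tumors and metastasis at 6 months follow up". The Study Summary and Section 3.1 carry the same promise.
- **Reference standard.** The Study Summary states: "In the pilot trial, the prostatectomy pathology will serve as the reference standard". No other reference is named for this arm.
- **6-month visit.** In Section 3.4.2, the RP calendar has a column for "6 months (+/- 1.5 months) following Prostatectomy". Two rows are marked there: "PSA Lab Result" and the adverse event review. Neither imaging nor biopsy is marked. Section 3.4.1 leaves postoperative care to standard practice.
- **Analysis.** Section 6.2 frames the main hypothesis per lesion, expects an average of 6 lesions per patient, and takes its power from the HIFU cohort. The test and the confidence interval it specifies are both for sensitivities. Its secondary-endpoint line names specificity for tumors on prostatectomy and gives no unit or method.
- **Sections.** Section 6.1 divides the prostate into six sections for the HIFU arm. Table 1, reprinted in Section 6.2, has a column that counts patients with a positive section.
- **Exploratory entry.** Section 3.3 also lists "Sensitivity and specificity of PET-hrMRI for detecting all tumors detected on prostatectomy pathology".

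**The concern.** Specificity is the share of reference-negative units that imaging also calls negative. It needs a reference test that identifies the negatives and a unit in which they can be counted. For metastasis the plan supplies no reference test. For tumors it supplies the reference, but the only unit Section 6.2 states cannot produce negatives.

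Section 2.9 justifies the RP arm by saying that knowing every tumor's location allows both sensitivity and specificity to be determined. If the unit is settled after the data are seen, the denominator, and with it the reported specificity, can depend on that choice. If the metastasis wording stays, the final report must either leave out a stated endpoint or improvise a reference from one PSA value.

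**Working it through.** The plan prints no figure for specificity, so there is none to reproduce. Table 1 concerns sensitivity and says nothing about this endpoint. Its patient column does follow from the stated 82%: 0.82 × 30 = 24.6, printed as 25.

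**Metastasis.** Specificity = TN / (TN + FP), and both cells consist of men verified as free of metastasis. Prostatectomy pathology describes the gland at surgery, not metastasis status six months later. The visit yields one PSA result per man with no rule attached. Verified negatives under the written plan: 0 of 31.

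If a reference were named and all 31 men proved negative with no false positive (assumed), the exact 95% interval would be 88.8% to 100%. With one false positive it would be 83.3% to 99.9%.

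**Tumor specificity, by unit.**
- *Lesion.* Lesions on pathology are all reference-positive. The only identifiable negatives are false-positive calls, so TN cannot be counted.
- *Patient.* Men scheduled for prostatectomy have cancer, so there are essentially no negatives.
- *Section.* 31 × 6 = 186 sections. The number negative depends on an assumption:

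| Assumption | Arithmetic | Negative sections |
|---|---|---|
| 2.5 positive sections per man (Section 6.1's lesion average) | 31 × (6 − 2.5) | about 108 |
| 2.5 averages over all patients, including the 18% with none | 2.5 / 0.82 = 3.05; 31 × (6 − 3.05) | about 91 |
| exactly 6 lesions per man, placed at random | 186 × (5/6)^6 | about 62 |
| 6 lesions, each in its own section | 31 × (6 − 6) | 0 |

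**Precision once sections are adopted.** Half-width = 1.96 × √(0.85 × 0.15 / N × D), where D = 1 + (N/31 − 1) × r. The 85% specificity and the within-man correlation r are assumptions. The two negative values are Section 6.1's within-patient correlations; they concern lesions, so they only bracket the range.

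| r | N = 108 | N = 62 |
|---|---|---|
| −0.249 | 4.2 points | 7.7 points |
| −0.119 | 5.7 | 8.3 |
| 0 | 6.7 | 8.9 |
| 0.3 | 8.9 | 10.1 |

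**Outside-hospital surgery.** Section 3.4.1 assures only the pathology report and leaves slide review undecided. If 5 or 10 of the 31 cases (assumed) could not be assigned to sections, 108 would fall to 26 × 3.5 = 91 or 21 × 3.5 = 73.5.

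**The case against.** The strongest reply concerns tumors. Six sections are stated in Section 6.1, Section 6.2 borrows that power, and the table reprinted there counts patients by positive section. The 6 lesions in Section 6.2 may be loose wording for six evaluated sections; if so, the 62 and 0 rows fall away. Section 2.9 also reasons from tumor location. This stands. A reader might infer that the whole endpoint is undeliverable, but the documents do not support that for tumors: the unit can be inferred and the reference exists. What is missing is its adoption for specificity and an interval method.

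Two further inferences about metastasis should be resisted. Section 6.2's secondary-endpoint line ends at a break in the text, so its silence on metastasis may not be deliberate. The one scan description says the participant "will be scanned in the area of the prostate", but it sits under the pre-HIFU heading, and no separate RP scan field is shown. Neither is needed: the missing reference test is enough.

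It is also fair that the half-widths describe precision after the repair, under assumed inputs. They do not measure the defect. Finally, Section 9.0 shows that the 6-month RP procedures were added in the latest amendment, so the sponsor may prefer to define a reference instead of dropping the component.

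**Conclusion.** The metastasis component cannot be estimated as written, because the plan supplies no verified negatives. This rests on the documents alone and needs no numerical assumption.

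Tumor specificity is under-specified but recoverable. The stated lesion unit gives no true negatives, while the inferable section unit gives 186 sections. About 108 of these are negative if 2.5 per man are positive; that count, and any interval width, rests on assumptions.

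A reader might carry this over to the primary analysis. The documents do not support that: the sensitivity comparison needs only reference-positive units. How the imaging combination is defined, which lesion count is right for power, and whether the exploratory PET-hrMRI entry should be promoted are separate matters. The change should be made before the RP data are analyzed.

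**What to change.** 1. In the Study Summary, Section 3.1 and Section 3.3, remove the metastasis-at-6-months clause and report the scheduled PSA descriptively as its own item. If the sponsor keeps the component, name the reference that verifies presence and absence of metastasis. Removal costs a claim that the schedule cannot support.
2. In Section 6.2, define tumor specificity on the six prostate sections, with sections free of carcinoma on prostatectomy pathology as the denominator. Report it for hrMRI, PET and mpMRI, each with a 95% interval that allows for clustering within a man. Give the difference from mpMRI with the clustered matched-pair interval already cited as reference 18.
3. Report how many outside-hospital cases cannot be assigned to sections.

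Items 2 and 3 cost wording and the work of mapping surgical pathology to six sections. Section 2.5 reports that the team's earlier study scored imaging by zone against biopsy, so the approach is familiar, but the surgical specimen needs its own mapping rule. Cases that cannot be mapped reduce precision.
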